The Structured Clinical Interview for DSM-5 – Clinical Trials Version (SCID-5-CT) will be employed for the determination of MDD and will be performed by a qualified, trained, validated healthcare professional.

Qualified staff will also complete the Montgomery-Åsberg Depression Rating Scale (MADRS), Hamilton Anxiety Rating Scale (HAM-A), Clinical Global Impression-Severity (CGI-S), Columbia-Suicide Severity Rating Scale (C-SSRS), and Childhood Trauma Questionnaire (CTQ).

Ophthalmic exams, including slit-lamp imaging, may be performed by an appropriately trained and qualified individual as delegated by the PI and documented in the Study Delegation Log. However, a licensed ophthalmologist or optometrist must oversee this work and will make the

determination on subject eligibility as per inclusion criteria #4. Slit lamp imaging of the lens of both eyes will be taken and sent to a central reader for assessment using the LOCS III classification.

Study site personnel will dispense equipment for 12-hour urine collection to measure cortisol levels.

A call between the subject and the qualified central rater will be scheduled to allow the rater to administer the Massachusetts General Hospital Antidepressant Treatment Response Questionnaire (MGH ATRQ) for assessment of current antidepressant therapy (ADT), adequacy of duration and dose of prior and current ADT, as well as degree of improvement, to ensure only patients with inadequate response (<50% improvement) are included. The central rater will also complete the MADRS assessment and SAFER inventory (State vs trait, Assessability, Face and Ecological validity, Rule of 3Ps [pervasive, persistent, and pathological]) for confirmation of eligibility (diagnosis, severity, and treatment history). Results will be communicated to the site prior to Day 1.

No changes to medications are allowed during the screening period, and screening can be less than 30 days if all other criteria are met.

Open-Label Treatment Period (Days 1, 8, 15, 29, 43, 56)

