5.1. Inclusion Criteria

Patients who meet ALL the following inclusion criteria will be eligible to participate in the study:

- 1. Demonstrate understanding of the study procedures, restrictions, and willingness to participate as evidenced by voluntarily signing and dating the written informed consent form.
- 2. Adult male or female between 18 and 65 years of age, inclusive.
- 3. Good physical health and has no clinically significant findings, as determined by the Investigator, on physical examination, 12-lead electrocardiogram (ECG), vitals, or clinical laboratory tests.
- 4. Has no clinically significant findings on the ophthalmic examination, including Best Corrected Visual Acuity (BCVA) worse than 20/30 or, in the opinion of the ophthalmologist or optometrist, any cataract that may become clinically significant and/or need surgical intervention during the course of the trial.
- 5. Able and willing to complete all study requirements.
- 6. Diagnosis of current episode of major depressive disorder (MDD) at least 8 weeks prior to screening confirmed by Structured Clinical Interview for DSM-5 Clinical Trials Version (SCID-5-CT).
- 7. Have not responded to their current antidepressant therapy or to dose adjustment/treatment changes following a loss of response to their current antidepressant therapy.
- 8. Complete the SAFER interview, administered via teleconference by a Massachusetts General Hospital (MGH) psychiatrist or psychologist, and receive a passing score which confirms a diagnosis of MDD, and a minimum Montgomery-Åsberg Depression Rating Scale (MADRS) total score of 26. The SAFER interview will also confirm the subject's treatment history and response to antidepressant therapies (ADTs) through the administration of the MGH Antidepressant Treatment Response Questionnaire (ATRQ).
- 9. Receiving a stable dose of the same antidepressant (selective serotonin reuptake inhibitor [SSRI], serotonin and norepinephrine reuptake inhibitor [SNRI], bupropion or trazodone monotherapy) for the current episode for at least 6 weeks of continuous treatment, which can include some or all of the screening period, with 4 weeks on a stable dose prior to day 1 and has an inadequate response (<50% improvement) using the MGH ATRQ.
- 10. Willing to maintain stable dose and delay start of other antidepressant or antianxiety medications and any new pharmacotherapy regimens, including benzodiazepine anxiolytics, during the screening and treatment periods.

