## **5.1. Handling Missing Data**

For incomplete dates related to adverse events and concomitant medications, the dates will be imputed as follows:

- Incomplete start dates missing day with known month will be imputed as the later of (a) day of first dose started in that month or (b) first of the month.
- Incomplete start dates missing month and day will be imputed as the later of (a) month and day of first dose started in that year or (b) January 1.
- Dates missing year regardless of month or day will be considered as missing.
- An unknown start time with known or imputed date will be imputed with a time of 23:59 for events or medications on Day 1 or as 00:00 on other days.
- An unknown end time with known or imputed date will be imputed the same as a missing start time unless the event or medication is ongoing.
- Events with completely unknown start dates will be considered as treatment-emergent adverse events unless otherwise indicated by a known end date.
- Medications with completely unknown start dates will be considered as concomitant medications unless otherwise indicated by a known end date.
- Any imputed start date or time must come before any known end date or time.
- Missing dates, date parts, and time will be shown as missing in the listings.

For missing values not described in this section of the SAP, imputation will not be performed.

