## **5.2. Definitions**

- The baseline measurement for a variable is defined as the most recent non-missing value prior to study treatment.
- The change from baseline measurement for a variable at a post-baseline visit will be derived as the measurement taken at the specified visit minus the baseline measurement.
- Treatment Duration will be derived as the total number of days on treatment as follows: Date of Last Dose – Date of First Dose + 1.

- Study Duration will be defined as the total number of days in the study as follows: Date of Last Visit – Date of Informed Consent + 1.
- Treatment Period is defined to be the period that the subject is active on treatment: Date of First Dose through Date of Last Dose.
- Treatment Compliance over the Treatment Period will be calculated as follows based on drug accountability: Treatment Compliance (%) = Number of capsules taken / Number of capsules expected to be taken  $\times$  100.
- Morning Meal Compliance over the Treatment Period will be calculated as follows based on Day 1 administration and the dosing diary: Morning Meal Compliance is Yes if all responses to the following questions are yes; otherwise, Morning Meal Compliance is No:
  - Was subject dosed at least 1 hour prior to morning meal?
  - Since last visit, has subject been compliant with dosing at least 1 hour prior to the morning meal?
- MADRS responders are defined as subjects who experienced a  $\geq$  50% reduction in MADRS total score compared to baseline.
- MADRS remitters are defined as subjects with a MADRS total score  $\leq$  10.
- CGI-I improvers are defined as subjects who reported “Very much improved” or “Much improved” on the CGI-I scale.
- An adverse event is defined as Related if the event is reported as Definitely Related, Probably Related, or Possibly Related.
- Adverse Events of Special Interest are defined as a change from baseline of  $\geq$  0.5 in Nuclear Opalescence, Cortical Lens Opacity, or Posterior Subcapsular Lens Opacity on the LOCS III scale, or any other ophthalmic results deemed clinically significant by the investigator.
- Age at First MDD Diagnosis will be calculated as follows: Year of the First MDD Diagnosis – Year of Birth, where the Year of the First MDD Diagnosis is defined as the year from the earliest start date of the major depressive episodes determined in Section 7.4 of this SAP.

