- Number of Prior MDD Episodes will be calculated as follows: The number of MDD Episodes with a Start Year that is prior to the Year of the Day 1 Visit,

where MDD Episodes are defined as the major depressive episodes determined in Section 7.4 of this SAP.

- Duration of Current MDD Episode will be calculated as follows: Year of the Day 1 Visit – Start Year of the Current MDD Episode, where the Start Year of the Current MDD Episode is defined as the year from the most recent start date prior to the Day 1 Visit of the major depressive episodes determined in Section 7.4 of this SAP.
- Duration from First MDD Diagnosis will be calculated as follows: Year of Day 1 Visit – Year of the First MDD Diagnosis, where the Year of the First MDD Diagnosis is defined as the year from the earliest start date of the major depressive episodes determined in Section 7.4 of this SAP.

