#### **7.4. Baseline Major Depressive Disorder Characteristics**

Major depressive episodes will be determined by using the Medical Dictionary for Regulatory Activities (MedDRA) coded terms of “Depression” and “Major depression” from medical history. The Age at First MDD Diagnosis (years), Number of Prior MDD Episodes, Duration of Current MDD Episode (years), and Duration from First MDD Diagnosis (years) will be calculated as defined in Section 5.2 of this SAP.

A summary will be provided for the Age at First MDD Diagnosis, Number of Prior MDD Episodes, Duration of Current MDD Episode, Duration from First MDD Diagnosis, baseline MADRS total score, and baseline HAM-A total score using the safety population.

A listing of major depressive episodes from medical history with their start and end dates, identified by the aforementioned MedDRA coded terms, and the Age at First MDD Diagnosis, Number of Prior MDD Episodes, Duration of Current MDD Episode, and Duration from First MDD Diagnosis will also be provided.

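### Duration of the current depressive episode is a difference of calendar years, so individual values can be wrong by almost a year either way and an eligible subject can show 0

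*SAP*

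**What the plan says.** SAP 5.2 gives the formula: "Duration of Current MDD Episode will be calculated as follows: Year of the Day 1 Visit – Start Year of the Current MDD Episode". The start year comes from medical history: "Start Year of the Current MDD Episode is defined as the year from the most recent start date prior to the Day 1 Visit". SAP 7.4 summarises the result in years for the safety population, next to age at first diagnosis, number of prior episodes and duration from first diagnosis. It also plans "A listing of major depressive episodes from medical history with their start and end dates".

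Two other parts of the SAP matter here. Treatment duration, in the same definitions section, uses full dates: "Date of Last Dose – Date of First Dose + 1". The partial-date rules in SAP 5.1 are limited in scope: "For incomplete dates related to adverse events and concomitant medications, the dates will be imputed as follows". That section then rules out imputation of any missing value it does not describe, so medical-history dates have no rule.

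Protocol 5.1 sets the floor on episode length: "Diagnosis of current episode of major depressive disorder (MDD) at least 8 weeks prior to screening". Protocol 4.1 adds that "screening can be less than 30 days if all other criteria are met". The SAP plans no covariate adjustment (6.2) and no subgroup analysis (6.4).

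**The concern.** The entry criterion is stated in weeks, but the derived duration moves only in whole calendar years. Two subjects with the same episode length can receive different values because of where Day 1 falls in the year, and a shorter episode can be recorded as longer than a longer one. A value of 0 also sits oddly beside an entry criterion of at least 8 weeks.

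What is at stake is a baseline descriptor. In a single-arm trial of up to 20 subjects, readers use the baseline table to judge how chronic the sample is and to compare it with other populations. The SD, median and range are built from the individual values, and a median of whole numbers can only fall on a whole or half year.

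**Working it through.** The plan states no figure on this point, so there is nothing to reproduce. The check applies the SAP formula to dates and compares the result with the elapsed time.

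**Shortest eligible episode.** 8 weeks before screening is 56 days. Screening ends at Day -1, so Day 1 is at least one day later: 56 + 1 = 57 days.

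**Two illustrative subjects** (dates assumed):

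| Episode start | Day 1 | Days | Days/365.25 | SAP value |
|---|---|---|---|---|
| 18 Nov 2022 | 20 Jan 2023 | 63 | 0.17 | 2023 − 2022 = 1 |
| 5 Jan 2022 | 28 Dec 2022 | 357 | 0.98 | 2022 − 2022 = 0 |

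The order of the two is reversed. Over the 365 possible Day 1 dates in a year, a 63-day episode is recorded as 1 on 63 dates (17%) and as 0 on the rest. A 357-day episode is recorded as 0 on 8 dates (2%, the end of December) and as 1 on the rest.

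**What a recorded value can mean** (non-leap years). A 0 needs both dates in one calendar year: 57 to 364 days. A 1 needs adjacent years: 57 to 729 days. Recorded minus true lies between about −1 and +1 year.

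**Average size.** Assume Day 1 is uniform over the year, and write the true length as *k* + *f* years, with *k* whole and 0 ≤ *f* < 1. The SAP value is *k* with probability 1 − *f* and *k* + 1 with probability *f*. Then, for a given length:

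- Expected recorded value = *k* + *f*, so the mean is unbiased.
- Expected absolute error = (1 − *f*)·*f* + *f*·(1 − *f*) = 2*f*(1 − *f*).
- Probability of an error of at least half a year = min(*f*, 1 − *f*).
- Variance added to the true variance = *f*(1 − *f*).

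These are averaged over true length. The documents give no distribution, so three uniform ranges are assumed. For 2 to 12 months:

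- Mean absolute error: the integral of 2*f*(1 − *f*) from 1/6 to 1 is 0.3086; divided by 10/12 this is 0.370 years = 4.4 months.
- SD: true variance (10/12)²/12 = 0.0579; add 0.370/2 = 0.185; total 0.243; square root 0.493 years = 5.92 months.

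Each further full year of range adds 1/3 to the first integral. A simulation gives the same values.

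| Assumed range (months) | Mean abs. error (months) | Off by ≥ 6 months | Recorded as 0 | SD recorded vs true (months) | Mean recorded vs true (months) | Correlation with true |
|---|---|---|---|---|---|---|
| 2–12 | 4.4 | 28% | 42% | 5.92 vs 2.89 | 7.0 vs 7.0 | 0.49 |
| 2–24 | 4.2 | 27% | 19% | 8.10 vs 6.35 | 13.0 vs 13.0 | 0.78 |
| 2–60 | 4.1 | 26% | 7% | 17.46 vs 16.74 | 31.0 vs 31.0 | 0.96 |

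The error per subject is about 4 months in every row. The effect on the SD and the share recorded as 0 both fall sharply as the range widens.

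**The case against.** The strongest reply is that nothing inferential uses this variable. It appears in one table and one listing, and with up to 20 subjects the listing shows each episode's start date, so a reader with access to it can recover a finer duration wherever one was recorded. That stands, and it sets the weight of the point.

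Year precision may also be deliberate. All the depression-history definitions use years, and patients often recall onset only roughly. The SAP does not say that medical-history dates are complete. This is a plausible reading, but the SAP does not state it, and it would not justify discarding month and day where they are known.

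A reader might infer more than the documents support:

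- *That the SD is doubled.* This holds only for the 2–12 month range. It is about 1.3 times the true SD for 2–24 months and 1.04 times for 2–60.
- *That values will be mostly 0 or 1 because episodes here last months.* The documents give a floor of 8 weeks and no upper limit. Exclusion 3 admits up to two failed antidepressants of at least 6 weeks each in the episode, besides the current one. Under 2–60 months only 28% of values would be 0 or 1.
- *That the variable records enrolment month rather than duration.* The correlation with true duration is 0.49 to 0.96.
- *That the mean is biased.* It is not, if Day 1 dates are spread evenly over the year.
- *That long episodes are routinely recorded as 0.* The 51-week example needs Day 1 in the last 8 days of December.

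**Conclusion.** The point holds as a matter of precision in a baseline descriptor. The stated rule gives wrong values for individual subjects even when the dates are known, and nothing else in the plan corrects it. The ranges of 57 to 364 days for a recorded 0 and 57 to 729 days for a recorded 1 follow from the formula and the entry criterion alone. The average error of 4.1 to 4.4 months and the 26 to 28% of subjects off by 6 months or more rest on assumed uniform durations and evenly spread Day 1 dates. The SD inflation depends on the assumed range and should not be quoted as one figure.

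A reader might take this as a threat to the efficacy conclusion or to who was enrolled. It is neither: the variable is not a covariate, a subgroup factor or an input to the primary MADRS analysis, and eligibility is confirmed separately by interview.

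**What to change.** 1. **SAP 5.2.** Define the duration as (Day 1 date − current-episode start date)/365.25, in years to at least one decimal. Alternatively report months and change the unit in 7.4 to match. The two illustrative subjects then read 0.17 and 0.98 years in place of 1 and 0.
2. **SAP 5.1.** Add a partial-date rule for these medical-history dates. If only the day is missing, use mid-month. If only the year is known, use the earlier of mid-year and the midpoint between 1 January and the latest onset compatible with Day 1 and the 8-week criterion. Flag imputed values. The cap is needed because plain mid-year imputation can put onset after Day 1. For example, with a start known only as 2023, screening on 14 March 2023 and Day 1 on 15 March 2023, the latest compatible onset is 17 January, the midpoint is 9 January and the duration is 65 days. If the latest compatible onset falls before the recorded start year, query the record instead of imputing.
3. **Duration from First MDD Diagnosis.** Use the same date arithmetic, so that the two durations agree for a subject in a first episode.

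The cost is two changed definitions, one extra imputation rule and some flagged values. While 5.2 is open, Number of Prior MDD Episodes also deserves a look: its comparison of years counts a current episode that began in an earlier calendar year as prior.

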## **6. Analysis Considerations**

The objectives of this study are to evaluate the safety and tolerability, and to evaluate the efficacy, of ANC-501 capsules in subjects with MDD.

### **6.1. Determination of Sample Size**

Up to 20 subjects will be enrolled. The sample size was selected based on clinical and not statistical considerations.

### **6.2. Adjustments for Covariates**

No adjustment for covariates is planned.

### **6.3. Interim Analysis and Data Monitoring**

No interim analyses are planned.

### **6.4. Examination of Subgroups**

No subgroup analyses are planned.

### **6.5. Multicenter Studies**

All sites will be pooled for this analysis.

### **6.6. Multiplicity Comparison/Multiplicity**

Not Applicable.

## 7. Population Analysis

The subjects will be summarized using descriptive statistics. All population summaries will be based on the set of subjects mentioned in the relevant section of this SAP.

Results for population parameters will also be listed by subject according to the relevant section in this SAP.

### 7.1. Subject Disposition

Information regarding subject disposition will be summarized using all subjects. Summaries will include the number of screen failures, the number of enrolled subjects, the number of subjects in the safety and efficacy populations, number of subjects completing the study treatment, number of subjects who discontinue the study treatment early, number of subjects completing the study, and number of subjects who discontinue the study early. For those who discontinue the study treatment early or discontinue the study early, the primary reason for discontinuation will be summarized.

A listing of subjects showing screen failures, analysis populations, study treatment status, study status, reason for discontinuing study treatment early, if applicable, and reason for discontinuing the study early, if applicable, will also be provided. Additionally, a listing of inclusion/exclusion criteria not met will be provided.

### 7.2. Protocol Deviations

Protocol deviations will be collected throughout the duration of the study. Protocol deviations will be assigned a sponsor-defined category and subcategory and classified as major or minor. A categorical summary of all major subject level deviations will be provided by deviation category and subcategory.

A listing of all subject level deviations will also be provided.

### 7.3. Demographic and Baseline Characteristics

Demographics variables will include age, sex and childbearing potential if females, race, ethnicity, height at baseline, weight at baseline, and BMI at baseline. Baseline characteristics will include the Montgomery-Åsberg Depression Rating Scale (MADRS) total score obtained at the SAFER screening interview and the Childhood Trauma Questionnaire (CTQ) subscale scores (Emotional Abuse, Physical Abuse, Sexual Abuse, Emotional Neglect, Physical Neglect) and CTQ Minimization/Denial scale score.

Demographics and baseline characteristics will be summarized for the safety and efficacy analysis populations, and a listing of demographics will also be provided.

#### **7.4. Baseline Major Depressive Disorder Characteristics**

Major depressive episodes will be determined by using the Medical Dictionary for Regulatory Activities (MedDRA) coded terms of “Depression” and “Major depression” from medical history. The Age at First MDD Diagnosis (years), Number of Prior MDD Episodes, Duration of Current MDD Episode (years), and Duration from First MDD Diagnosis (years) will be calculated as defined in Section 5.2 of this SAP.

A summary will be provided for the Age at First MDD Diagnosis, Number of Prior MDD Episodes, Duration of Current MDD Episode, Duration from First MDD Diagnosis, baseline MADRS total score, and baseline HAM-A total score using the safety population.

A listing of major depressive episodes from medical history with their start and end dates, identified by the aforementioned MedDRA coded terms, and the Age at First MDD Diagnosis, Number of Prior MDD Episodes, Duration of Current MDD Episode, and Duration from First MDD Diagnosis will also be provided.

#### **7.5. Screening Mental Health Assessments**

##### **7.5.1. Structured Clinical Interview for DSM-5 – Clinical Trials Version**

Subjects will be screened to determine whether they fulfill the criteria for diagnosis of MDD according to the Structured Clinical Interview for DSM-5 – Clinical Trials Version (SCID-5-CT). No listing or summary table will be provided.

##### **7.5.2. SAFER Interview**

The SAFER interview is conducted for confirmation of MDD. The interview uses the MADRS and also makes use of the Massachusetts General Hospital Antidepressant Treatment History Questionnaire (MGH ATRQ) for assessment of current antidepressant therapy (ADT), adequacy of duration, and dose of prior and current ADT, as well as degree of improvement. No listing or summary table will be provided.

##### **7.5.3. Childhood Trauma Questionnaire**

CTQ is assessed at screening only. It is a retrospective measure of childhood trauma and contains five subscales (Emotional Abuse, Physical Abuse, Sexual Abuse, Emotional Neglect, Physical Neglect) and a Minimalization/Denial scale. The results will be

presented in a listing. No summary table will be provided. The CTQ scores are addressed in Section 7.3 of this SAP.

